#### List of Abbreviations and Definitions of Terms

9-HPT	9 Hole Peg Test
ACTH	Adrenocorticotrophic hormone
ADA	Anti-drug antibody
ADME	Absorption, Distribution, Metabolism, Excretion
AE	Adverse event
AESI	Adverse event of special interest
ALT	Alanine aminotransferase
ANCOVA	Analysis of covariance
aPTT	Activated partial thromboplastin time
ARR	Annualized relapse rate
AST	Aspartate aminotransferase
ATC	Anatomic Therapeutic Chemical Classification
BART	Blinded Assessment Relapse Team
BMI	Body mass index
BOD	Burden of disease
BP	Blood pressure
BPF	Brain parenchymal fraction
BUN	Blood urea nitrogen
CNS	Central nervous system
CrCl	Creatinine clearance
CRF	Case report form
CSF	Cerebrospinal fluid
CSR	Clinical study report
DILI	Drug-induced liver injury
DMC	Data Monitoring Committee
DSMB	Data Safety Monitoring Board
EAE	Experimental allergic encephalomyelitis
ECG	electrocardiogram
EDSS	Expanded Disability Status Scale
EOPII	End of Phase II
EPTD	Early permanent treatment discontinuation
EQ-5D	EuroQoL (quality of life scale)

FIS	Fatigue Impact Scale
FS	Functional System
FSH	Follicle stimulating hormone
GCP	Good clinical practice
Gd	gadolinium
GEE	Generalized estimating equation
GGT	Gamma glutamyl transferase
Hb	hemoglobin
HCG	Human chorionic gonadotrophin
HIV	Human immunodeficiency virus
HLGT	High Level Group Term
HLT	High Level Term
HMR1726	Teriflunomide
ICH	International Council for Harmonisation
ICU	Intensive care unit
INR	International normalization ratio
IP	Investigational product
IRAP	Independent Relapse Adjudication Committee
ITT	Intent-to-treat
IVRS	Interactive voice response system
LOCF	Last observation carried forward
MedDRA	Medical Dictionary for Regulatory Activities
mITT	modified Intent-to-Treat
MMRM	Mixed-effect model with repeated measures
MRI	Magnetic resonance imaging or magnetic resonance image
MRI-AC	MRI analysis center
MS	Multiple sclerosis
MSFC	Multiple Sclerosis Functional Composite
MSQoL-54	Multiple Sclerosis Quality of Life-54
NEDA	No evidence of disease activity
PASAT	Paced Auditory Serial Addition Test
PCA	Predefined change abnormal
PK	Pharmacokinetic

PK/PD	Population pharmacokinetic/pharmacodynamic
PML	Progressive Multifocal Leukoencephalopathy
PP	Per Protocol
PR	Pulse rate
PS-MS	Performance Scales–Multiple Sclerosis
PT	Preferred term
RMS	Relapsing forms of Multiple Sclerosis
SAE	Serious adverse event
SAP	Statistical analysis plan
SD	Standard deviation
SDMT	Symbol Digit Modalities Test
SF-36	Short Form generic health survey (36 items)
SGGT	Serum gamma-glutamyl transferase
SGOT/AST	Serum glutamic oxaloacetic transaminase/aspartate aminotransferase
SGPT/ALT	Serum glutamic pyruvic transaminase/alanine aminotransferase
SMQ	Standardized MedDRA Queries
SOC	System Organ Class
T25-FW	Timed 25-Foot Walk
TEAE	Treatment emergent adverse event
VAS	Visual Analogue Scale
WBC	White blood cells
WHO-DD	World health organization drug dictionary
WPAI	Work productivity and activity impairment

# 1 Overview and Investigational Plan

This statistical analysis plan (SAP) provides a detailed description of the statistical strategy for the “TG1101-RMS302” protocol Version 5.0 dated 04 September 2020. The goal of the SAP is to pre-specify the statistical approaches to the analysis of study data prior to study initiation. It has been revised before database lock to cover protocol amendments and all technical aspects of the planned statistical analysis. Significant revisions and the corresponding rationale are summarized in Section 5 of this document.

## 1.1 Study Design and Randomization

This is a 120 week, Phase 3, randomized, multi-center, double-blinded, double-dummy, active-controlled study that is primarily designed to assess the annualized relapse rate (ARR) and safety/tolerability of ublituximab (TG-1101; UTX)/oral placebo as compared to teriflunomide/IV placebo in subjects with relapsing forms of Multiple Sclerosis (RMS).

After early termination of trial or at the end of study visit at Week 96, subjects will enter a 20 week follow-up program inclusive of the accelerated elimination of teriflunomide.

## 1.2 Objectives

### 1.2.1 Primary Objective

To determine the annualized relapse rate (ARR) in subjects with RMS after 96 weeks (approximately 2 years with a year is equal to 365.25 days) treatment with IV infusion of ublituximab/oral placebo compared to 14 mg oral teriflunomide/IV placebo.

### 1.2.2 Secondary Objectives

The secondary objectives are to examine the effects of ublituximab/oral placebo as compared to teriflunomide/IV placebo as follows:

1. On MRI parameters,
2. Confirmed Disability Progression (CDP),
3. No Evidence of Disease Activity (NEDA),
4. Symbol Digit Modality Test (SDMT)
5. To evaluate the safety of ublituximab/oral placebo, as determined by adverse events (AEs) and serious adverse event (SAEs), including MS worsening.

### 1.2.3 Tertiary Objectives

1. Change in MSFC score from baseline to Week 96
2. Time to Confirmed Disability Progression for at least 24 weeks
3. Time to Confirmed Disability Improvement for at least 12 weeks
4. Time to Confirmed Disability Improvement for at least 24 weeks
5. Health outcomes (MSQoL-54 (inclusive of SF36); FIS, hospitalization, steroid use, time out of work)
6. Total volume of Gd enhancing T1 lesions per MRI scan over the treatment period
7. Volume of T2 lesions
8. Volume of hypointense T1 lesion component (black holes)
9. Proportion of subjects free of disability progression at 24 weeks, 48 weeks, and 96 weeks
10. Proportion of subjects with a relapse
11. Time to first confirmed relapse

### 1.3 Determination of Sample Size

this required sample size is increased to 220 per group or a total randomized of 440.

#### 1.3.1 Interim Sample Size Reassessment

An independent committee, Blinded Assessment Relapse Team (BART), reporting to TG Therapeutics, and the DSMB will reassess the sample size for the study when 210 of the 220 participants have been randomized. Assuming a uniform rate of recruitment, we need an estimate as to how many person years of exposure will occur before an interim adjustment occurs. If recruitment is going to be accomplished in 8 to 10 months, the average exposure time when 210 subjects per group are recruited would experience half of the recruitment period or  $9/2=4.5$  months. We can use all of the data available at that time and thus will have approximately  $4.5 \times 210 = 945$  person months or approximately 43 person years of observation (the denominator to compute the ARR).

The Table below provides the sample sizes (total adjusted sample sizes) needed per group per study based on the findings at the interim (Columns of the Table) for reductions in the ARR of teriflunomide by 40%. As an example, if the estimated ARR in the pooled population is 0.20 and we are assuming an hypothesized 40% reduction in the ARR rate by ublituximab, then the ARR in the individual groups (red numbers in the table below) can be derived by solving a simple equation;  $(N_U * 0.6 P_T + N_T * P_T) / (N_U + N_T) = 0.20$  where  $P_T$  is the ARR in the teriflunomide group and  $N_T$  and  $N_U$  are the sample sizes, assumed to be equal. Thus, if the combined ARR=0.20, then this equation under the hypothesized reduction of 40% yields an estimated ARR of 0.25 in teriflunomide and 0.15 in ublituximab. Calculating the required sample size using a negative binomial comparison with 1.75 years of observation overall, results in an updated sample size of 219 per group. Thus, the original sample size of N=200 would be adjusted upward by adding 19 participants per treatment group, plus the 10% for dropouts yielding a total of 241 subjects per group or 21 additional participants.

In the Table below, which can guide the interim sample size reassessment, we see two color blocks in the table. The green area shows results that have two (2) characteristics - one, they require smaller sample sizes and two, they are unlikely to occur because the ARR rate in the teriflunomide group would have to exceed 0.31 (arbitrarily chosen, but some level is reasonable as an upper limit on what the rate is likely to be). Either way, if the blinded ARR falls in the green area or above, the sample size will not be reduced since we do not plan to reduce the sample size and 210 participants per group will have already been enrolled. The yellow area is the range for the combined total rates. If the overall ARR = 0.19 then the estimated teriflunomide rate would be estimated at 0.2375 and ublituximab would be estimated at 0.1425 and the sample size required would be 233 per group. Thus, a rate  $\leq 0.19$ , the sample size will be increased by 30 per treatment group in each study, but no more. Such observed relapse rates are quite low and unexpected, so that further adjustments are probably not warranted.

[figure not shown]
Recruitment will continue while the interim analysis is ongoing and if the participants recruited beyond the 220 per group will be used in the final analyses if the sample size is not increased and will count toward the additional sample size if warranted.

**Table 1 – Findings at Interim**

% Reduction in ARR	Treatment	Findings at Interim								
		0.160	0.180	0.200	0.220	0.240	0.260	0.280	0.290	0.300
40%	Ublituximab/ Oral Placebo	0.120	0.135	0.150	0.165	0.180	0.195	0.210	0.218	0.225
	Teriflunomide/ Placebo	0.200	0.225	0.250	0.275	0.300	0.325	0.350	0.363	0.375
Avg Follow-Up = 1.75 years	N	268	243	224	208	195	183	174	169	165

## 1.4 Study Plan

Refer to the study protocol for TG1101-RMS302 for study schedule for analysis variables.

## 2 Statistical and Analytical Procedures

### 2.1 Analysis Variables

#### 2.1.1 Demographics and Baseline Characteristics

All baseline safety and efficacy parameters (apart from the one listed below) are presented along with the summary statistics in the safety and efficacy sections ([Section 2.4](#)).

#### **Demographic and other baseline characteristics**

Demographic variables are gender (Male, Female), race (White, Black or African American, Asian, American Indian or Alaska Native, Native Hawaiian or Other Pacific Islander, Other, or Not Applicable due to country's legislation), age in years (quantitative and categorical variable: <38, and  $\geq 38$  years), Ethnicity (Hispanic or Latino, Not Hispanic or Latino, Not Reported, Unknown), country and region.

Regions are defined as follows:

- USA and Western Europe: USA, Spain, United Kingdom
- Eastern Europe: all other countries

Other baseline characteristics:

- Baseline hepatic function (normal, mild, moderate, or severe impairment)
- Baseline renal function (normal, mild, moderate, or severe impairment)

Classification of hepatic impairment per NCI-ODWG Criteria

Category	NCI-ODWG	
	Total Bilirubin	ALT or AST
Mild	B1: $\leq$ ULN	B1: $>$ ULN

	B2: >1-1.5x ULN	B2: Any
Moderate	>1.5-3x ULN	Any
Severe	>3x ULN	Any

#### Classification of renal impairment per EMA Guidance

Group	Description	GFR (ml/min)
1	Normal renal function	≥ 90
2	Mildly decreased renal function	60- <90
3	Moderately decreased renal function	30- <60
4	Severely decreased renal function	<30 not requiring dialysis
5	End stage renal disease (ESRD)	<15 requiring dialysis treatment

### **Medical and surgical history**

Medical history data will be coded to “Preferred Term (PT)” and associated primary “System Organ Class (SOC)” using the Medical Dictionary for Regulatory Activities (MedDRA) version 20.0. Dictionary upgrades are not planned during the course of the study.

### **Disease characteristics at baseline**

- Number of relapses experienced within past 1 year and 2 years (0, 1, 2, 3, and ≥4), respectively
- Time since first diagnosis of MS (in years) to be derived as (Day of randomization – Day of first MS diagnosis) / 365.25
- Time since first symptoms of MS (in years) to be derived as (Day of randomization – day of first symptoms of MS) / 365.25
- Time since most recent relapse onset (in months) to be derived as (Day of randomization – day of most recent relapse onset) / (365.25 / 12)
- Baseline EDSS score
- Baseline EDSS (≤3.5, >3.5)
- Number of baseline Gadolinium (Gd)-enhancing lesions (0, ≥1)
- Baseline T2 lesion count
- Baseline T2 lesion Volume
- Baseline brain volume

### **Multiple Sclerosis treatment history**

- Received any MS therapy for at least 1 month (30 days) prior to enrollment (Yes, No)
- MS therapy in the previous 5 years by Preferred Name
- Previous corticosteroid treatment for relapse
- Time since last corticosteroid treatment for relapse (months)

### **Vital signs and height**

Vital signs are variables: weight in kg (quantitative variable and categorical variable: <50, ≥50 - <100, ≥100), height (m) and Body Mass Index (BMI) in weight[kg]/height[m^2] (<30, ≥30) calculated from weight and height.

## **Prior or concomitant medications or Follow-Up Medications**

All medications taken within 3 months (5 years for previous MS treatments) before randomization and until the end of the study are reported in the case report forms (CRF).

All medications will be coded using the World Health Organization-Drug Dictionary (WHO-DD).

- Prior medications are those taken prior to first dose of treatment, either stopped before study treatment start or continuing.
- Concomitant medications are those taken at any time during the study treatment period, from the first study treatment use to the day of last study drug treatment, started before or during study treatment.
- Follow-up medications are those taken at any time between last study treatment and end of follow-up,

Technical details related to calculating dates, imputation for missing dates, etc. are described in Section 2.5.

### 2.1.2 Duration of Study Treatment Exposure and Compliance

#### **Duration of oral study treatment exposure**

Duration of treatment exposure (to oral study treatment teriflunomide/placebo) will be derived as:

(Date of Last oral Study Treatment - Date of First oral Study Treatment + 1).

In addition, duration of treatment exposure will also be categorized using the following intervals:

- $0 < \text{Duration} \leq 4$  weeks
- $4 < \text{Duration} \leq 12$  weeks
- $12 < \text{Duration} \leq 24$  weeks
- $24 < \text{Duration} \leq 48$  weeks
- $48 < \text{Duration} \leq 72$  weeks
- $72 < \text{Duration} < 96$  weeks
- $\text{Duration} \geq 96$  weeks.

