In case of an IRAP-confirmed MS relapse (as defined in the protocol, Appendix C) or Treating Neurologist medically confirmed relapse during the study, the following actions will be taken:

- The subject will be reminded of the current approved MS medications/treatments and the opportunity to terminate the study and be treated with an approved MS medication.
- The subject will be requested to re-sign an informed consent form within 6 weeks after first reporting of the suspected relapse if he/she chooses to continue to participate in the study, in the same treatment assignment.

[figure not shown]
Disability Progression

The method of disability progression calculation will be different than that of the relapse confirmation. The EDSS score will be used to assess disability progression. EDSS assessment will be performed by the Examining Neurologist. The Examining Neurologist must not share the EDSS score with the Treating Neurologist. The EDSS assessment for disability progression will be performed at screening and on Week 1 Day 1 (prior to randomization) and Weeks 12, 24, 36, 48, 60, 72, 84 and 96. To clarify, disability progression is not calculated by the Examining Neurologist (disability progression is a post hoc analysis based on the EDSS scores).

Disability progression is defined as an increase of ≥ 1.0 point from the baseline EDSS score that is not attributable to another etiology (e.g., fever, concurrent illness, or concomitant medication) when the baseline score is 5.5 or less, and ≥ 0.5 when the baseline score is above 5.5. Disability progression is considered confirmed when the increase in the EDSS is confirmed at regularly scheduled visits at least 12 or 24 weeks after the initial documentation of neurological worsening.

Treatment Study Visits

Ublituximab/oral placebo vs Teriflunomide/IV placebo Regimen (please see dosing regimen below)

- Ublituximab or IV placebo: Infusions on Week 1 Day 1 and Week 3 Day 15 and Weeks 24, 48, and 72
- Teriflunomide or oral placebo: Daily starting at Week 1 Day 1 until the last day of Week 95

Abbreviated Blood Sample Assessment Schedule (for further details see Section 6):

- For all subjects treated:
 - Blood collection for CBC and serum chemistry at screening, and Week 1 Day 1 (pre-dose), Week 1 Day 2, Week 2 Day 8, Week 3 Day 15 (pre-dose), and Weeks 4, 8, 12, 16, 20, 24 (pre-dose), 36, 48 (pre-dose), 60, 72 (pre-dose), 84 and 96

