4.5 DURATION OF THERAPY

For subjects randomized to ublituximab or treated with IV placebo, infusion will occur on Week 1 Day 1, Week 3 Day 15, and Weeks 24, 48 and 72.

For subjects randomized to teriflunomide or treated with oral placebo, administration may be taken in the morning until the last day of Week 95. Alternative dosing times are allowed if necessary.

If the subject discontinues the study, the reason for study removal and the date the subject was removed must be documented in the eCRF. Subjects who discontinue treatment due to an adverse event should be followed until resolution of the adverse event, unless the event is considered by the Treating Neurologist/PI to be due to the subject's underlying disease.

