7.5.1.1 GUIDELINES FOR ORAL TREATMENT OF TERIFLUNOMIDE OR ORAL PLACEBO

- *Necessity of MS Center/Neurology Department:* Center must have personnel and equipment necessary to provide adequate emergency treatment.

- Subjects who withdraw from treatment should be followed up for 20 weeks inclusive of the 11-day accelerated teriflunomide elimination procedure, during which they receive cholestyramine or activated charcoal.
- If a pregnancy is confirmed, the trial drug(s) must be immediately and permanently stopped, the subject must be discontinued from the trial, and the Treating Neurologist must report this to pharmacovigilance as soon as possible. Further, the subject needs to undergo immediate accelerated washout with either oral cholestyramine or oral activated charcoal and be followed for AEs for 20 weeks after their last dose of the trial drug (please see Section 6.10.1).
- Teriflunomide or oral placebo shall be taken each in the morning daily until the last day of Week 95. Alternative dosing times are allowed if necessary.
 - On Week 1 Day 1, teriflunomide or oral placebo dosing should occur upon completion of infusion. If vomiting occurs during the infusion of ublituximab or IV placebo, refrain from administering teriflunomide or oral placebo on Week 1 Day 1. The first dose of teriflunomide or oral placebo will be administered on Week 1 Day 2.
- Compliance to administration of teriflunomide or oral placebo
 - Plasma samples to determine the concentration of teriflunomide will be obtained from all subjects at the following time-points: Week 1 Day 1 and Week 48 (pre-infusion of ublituximab or IV placebo), and Week 96 or Early Withdrawal from Treatment Visit and Week 116.
 - The study sites will instruct the subjects enrolled into the study to return with their used and unused teriflunomide or oral placebo blister packs to the investigation site during every visit as shown in the Schedule of Assessments in Section 6 as part of the teriflunomide or oral placebo drug accountability assessment program. Compliance with teriflunomide or oral placebo administration will be reviewed with all subjects during those times by the study site and documented on the eCRF by the study site. A comment will be entered into the subject's subject diary and on the accountability log for any variation from the prescribed dosing schedule, such as additional or missed doses.

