8.9.1 PRIMARY EFFICACY VARIABLE

The primary efficacy variable will be Annualized Relapse Rate, defined as the number of relapses (protocol defined and confirmed by Independent Relapse Adjudication Panel) per subject-year (a year is equal to 365.25 days).

The primary efficacy analysis will be performed using the mITT with a Negative Binomial regression model to accommodate the potential over-dispersed data appropriately. The model will include the total number of confirmed relapses with onset between randomization date and the day of last study treatment as response variable, treatment group, EDSS strata (baseline EDSS score ≤ 3.5 versus > 3.5) and clinic region as covariates.

Relapses that occur after study drugs are withdrawn will be assessed over the remainder of the study period and this data will be utilized as part of additional sensitivity analysis (described in the statistical plan) as long as the subject has not withdrawn their consent to be in the trial.

The treatment group will have 2 levels (teriflunomide/ IV placebo or ublituximab/oral placebo). In order to account for different treatment durations among subjects, the log-transformed standardized treatment duration (randomization to date last treatment before early withdrawal or completion of Week 96 assessment) will be included in the model as an “offset” variable for appropriate computation of the Annualized Relapse Rate. [REDACTED] will be used to assess the overall model with subjects in a repeated statement using a Generalized Estimating Equation (GEE) approach.

Two-sided 95% confidence intervals of the rate ratio will be provided for the comparisons of Ublituximab/oral placebo versus teriflunomide/IV placebo. The estimated relapse rate and its 2-sided 95% confidence intervals will be provided for each treatment group.

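### The top oral-exposure category in SAP 2.1.2 starts at 96 weeks, but planned oral dosing ends with Week 95, so a completer dosed to plan is grouped with subjects who stopped just after Week 72.

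*SAP*

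**What the plan says.** SAP 2.1.2 derives the duration of oral exposure as "Date of Last oral Study Treatment - Date of First oral Study Treatment + 1". It then defines seven classes. The last two are more than 72 but less than 96 weeks, and 96 weeks or more. SAP 2.4.6 says that exposure is summarized in the safety population both as a continuous and as a categorical variable.

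The protocol fixes the planned oral course in several places. The synopsis (Treatment Study Visits) has "Teriflunomide or oral placebo: Daily starting at Week 1 Day 1 until the last day of Week 95", and Section 4.5 says "administration may be taken in the morning until the last day of Week 95". The dosing tables give the same end for teriflunomide and for oral placebo. Protocol Appendix F places the Week 96 visit on Day 672 and lists no treatment at it.

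The start can also move. If the subject vomits during the first infusion, Protocol 7.5.1.1 says "The first dose of teriflunomide or oral placebo will be administered on Week 1 Day 2".

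**The concern.** The class boundary appears to follow the nominal 96-week treatment period, which is counted to the Week 96 visit. The formula counts from first to last tablet, and the last planned tablet comes before that visit. The class meant to show full-duration exposure is then out of reach for a subject who follows the protocol exactly.

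The stake is the readability of a pre-specified safety table. It could not separate a subject with the full oral course from one who stopped soon after Week 72. It would also sit oddly beside the disposition table (SAP 2.3), which counts subjects who finished the 96-week treatment period. SAP 2.4.5.2 asks for abnormal liver tests to be displayed by duration of exposure. It does not say which duration classes to use, but those in SAP 2.1.2 are the only ones the SAP defines. If they are reused, the same merging enters the hepatic display, and Protocol 7.1.1.1 lists raised ALT as very common with teriflunomide.

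**Working it through.** **Inputs**
- Exposure formula and class limits: SAP 2.1.2.
- Planned oral course, Week 1 Day 1 to the last day of Week 95: Protocol synopsis, 4.3, 4.5 and 7.5.1.1.
- Week 96 visit on Day 672, no treatment: Protocol Appendix F. SAP 2.5.3 also targets Day 672.
- Permitted Day 2 start: Protocol 7.5.1.1 and 7.5.3.
- Visit window of 5 days either side from Week 8: Protocol Section 6, footnote 4 to Tables 5 to 7.
- Tablets per 12 weeks, 112 supplied and about 84 taken, so about 28 spare: Protocol 7.4.1.

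**Step 1: the plan's own figure.** 96 weeks × 7 = 672 days, which matches Day 672. The rule day = 7 × week also holds at Weeks 4, 8, 12, 24, 48, 72, 84, 100 and 116. The top class therefore needs at least 672 days.

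**Step 2: exposure of a subject dosed to plan.** With Week 1 as Days 1 to 7, Week 95 ends on Day 95 × 7 = 665. The widest reading of the calendar lets Week 96 begin at its visit on Day 672, so that the last planned tablet is on Day 671. Apply last − first + 1:

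| Case | First day | Last day | Days | Weeks | Short of 672 by |
|---|---|---|---|---|---|
| Dosed to plan | 1 | 665 | 665 | 95.00 | 7 |
| First tablet on Day 2 | 2 | 665 | 664 | 94.86 | 8 |
| Widest calendar reading | 1 | 671 | 671 | 95.86 | 1 |

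All three fall in the class between 72 and 96 weeks.

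**Step 3: who shares that class.** A subject whose last tablet is on Day 505 has 505 days, or 505/7 = 72.14 weeks. That is the same class, although the course is 665 − 505 = 160 days shorter than planned.

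**Step 4: who can reach the top class.** The last tablet must be on Day 672 or later for a Day 1 start, which is 7 days past the planned end. For example, a subject who keeps taking tablets until the day before a Week 96 visit held on Day 677 has 676 days, or 96.57 weeks. The spare tablets make this possible. SAP 2.5.1.2 also imputes an incomplete last-dose date to the end of the month or year, capped at study completion or discontinuation, and this can carry a subject over the cut.

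**The case against.** The strongest reply is that little depends on these classes, and most of it stands:
- Oral duration is also summarized with mean, SD, median, quartiles and range, and as cumulative subject-years (SAP 2.4.6). A median near 95 weeks would show full-course exposure directly.
- Disposition (SAP 2.3) separates completers from subjects who discontinued.
- In the ublituximab arm the tablets are placebo. Exposure to ublituximab is counted in infusions out of five (SAP 2.1.2), which is unaffected.
- The per-protocol cut of 1.75 years (1.75 × 365.25 = 639 days) lies below 664 days and does not use the classes.

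None of this corrects the boundary. It confines the harm to the categorical table and any display built on it.

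Three stronger readings are tempting, and the documents do not support them.

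1. A reader might infer that every completer is misplaced and that the top class will be almost empty. The arithmetic covers completers dosed to plan. Overruns and imputed dates can reach 672 days, and the documents give no way to count them. The 5-day window does not rescue the boundary either, since it is written for collections and assessments, not for the end of oral dosing.

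2. A reader might infer a matching error in the relapse-rate offset, because Protocol 8.9.1 describes treatment duration as "randomization to date last treatment before early withdrawal or completion of Week 96 assessment". The phrase can be read as running to the Week 96 assessment for completers. It can equally be read as the last treatment before either event, which agrees with the relapse window in the same section. SAP 2.1.3.1 and 2.4.2 settle it: both relapses and duration end at last treatment.

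3. A reader might infer that moving the cut to 95 weeks (665 days) solves the problem. It would misplace an adherent subject who starts on Day 2 and has 664 days.

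**Conclusion.** The mismatch is real. On the planned schedule a completer has 664 or 665 days of oral exposure, and no more than 671 on the widest reading, against a top class that starts at 672. The gap is 1 to 8 days. It is enough to place such a completer with subjects who stopped just after Week 72, in both arms.

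This rests on two assumptions: that the subject takes the last tablet no later than the planned day, and that the recorded dates are complete. For other subjects the top class can be reached, so it would hold mainly overruns and imputed dates.

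The consequence is limited to the categorical oral-exposure summary and, if the classes are reused there, the liver display by duration of exposure. The primary analysis, the secondary analyses, the analysis populations and the trial's conclusions do not depend on it. It is worth correcting because the fault can be seen from the schedule alone, and recutting the classes after unblinding would be a post hoc change.

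**What to change.** In SAP 2.1.2 and the matching table shell, reconcile the top two classes with the planned oral course. Either of two forms works:

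- Define the top class by completion, for example 'completed planned oral treatment (last oral dose on or after the last day of Week 95)', and state the study day taken as that last day. The class below then holds subjects with more than 72 weeks who did not reach it.
- Keep a numeric cut but set it to admit the permitted Day 2 start, for example 664 days or more, with the class below running from over 72 weeks to under 664 days. All three cases in the working (664, 665 and 671 days) then fall in the top class.

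SAP 2.4.5.2 should also say whether the liver display by duration of exposure uses these classes.

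The cost is one line in SAP 2.1.2, its table shell, and a cross-reference in 2.4.5.2. No dosing, data collection or efficacy analysis is touched.
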